11.4.2 Blinding

Both the placebo and the Icon materials are same in their delivery system, material color, and viscosity. Therefore, the investigators are blinded as to the material used, as are the patient and the evaluators.

11.4.3 Evaluation of Records

This section was revised and specified in Amendment 1 valid as of 30.11.2015!

The outcome variable will be the caries progression status (regression, no changes or progression) for the selected lesions after 3 years. The radiographs will be read by 2 methods (1) visual independent reading and (2) subtraction radiography of digitized images.

For visual readings the depth of each selected lesion will be visually assessed and recorded by the PI independently on the conventional baseline and follow-up radiographs, respectively. The depth of the selected lesion will be classified into the following scales 1- lesion regressed, 2- lesion expanded, 3 no change in lesion size. A score of 4 (missing surface, generally fractured) and 5 (presence of a restoration) may be assigned when needed. For all visual readings, the examiner will be blinded as to whether the examined radiograph was a radiograph of the lesion was Icon sealed or a control. The examiner will be asked to determine the status (1 to 5) of the right positioned image against the left positioned image of the radiograph.

To assess the progression status on subtraction images the conventional radiographs will be first digitized (Epson Expression 1680 Pro scanner, Photoshop software) in a standard way (TPU format, 8-bit, 3,200 resolution), and contrast and gamma levels will be pre-adjusted pair-wise in the baseline and follow-up images. The images will be stored uncompressed (TIFF 3,650 x 2,425 grayscale) at an individual size of 9–14 Mb. Next, the images will be converted to a readable format for the subtraction software in Adobe Photoshop 6.0 and stored as TIFF 600 x 400 files, with a code corresponding to case number, test/control lesion, baseline or follow-up and involved surface.

The digital subtraction of the digitized images will be undertaken by one of the examiners by means of the Compare software (Dental Health Unit, University of Manchester, UK), which runs as a plug-in to the Image Tool software, version 1.23 [University of Texas Health Science Center at San Antonio,

Texas, 2002]. The subtraction images will be obtained by subtracting the follow-up from the baseline images of each lesion. First, the two images will be automatically aligned to obtain a relationship with the least difference between them. The difference in density between the two images will then be normalized. Subtraction of images will be conducted, and the contrast stretched. The subtraction images will be coded and randomly organized, as described above, then saved in a Microsoft Powerpoint presentation. For their reading, the subtraction images will be viewed by an external trained examiner 10 days after the visual assessment of conventional radiographs. The presentation will be viewed on a 43.2-cm Hewlett Packard monitor in one session. Additionally, the examiner will be able to access the conventional baseline radiograph to confirm the vertical location of the lesion within the proximal surface. The subtraction progression will be observed as the presence of black points corresponding to an extension of the proximal lesion. Conversely, regression will correspond to the presence of white points and stabilization as an evenly grayish appearance on the image.

Intraexaminer reproducibility will be obtained by rereading 25% of the independent and paired radiographs and of the subtraction images 2 days after the first reading.

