6.2.2 Specific Aim II

Change in lesion size (Radiographic analyses)

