8.1 Baseline Records (*Radiographs*)

This section was revised and specified in Amendment 1 valid as of 30.11.2015!

Additional radiographs will not be taken for purpose of the trial only. The policy described below reflects the widely accepted, current best practice regarding detection, diagnosis and monitoring of approximal lesions. Standardized diagnostic bitewing radiographs will be taken using a standardized position device (DMG, Hamburg, Germany). The device facilitates optimal direction of the x-ray beam and thus leads to optimal diagnostic representation of the caries lesion.

Radiographic evaluation of the lesions and the quality of the adjacent enamel contact surface by standardized bitewing radiographs at baseline will be used to detect and diagnose the caries and monitor lesion change. An extensive review of the scientific evidence supports the importance of initial bitewings and radiographic recall examinations for description of caries progression.⁹⁻¹³ Both, the guidelines by Pitts and Kidd⁴ widely used in Europe, and the ADA/FDA-coordinated guidelines¹⁴ advise that in high risk children (age 10-16) the interval should be 6-12 month. The proposed timing of bitewings in our study (screening and at yearly intervals) falls well within these guidelines. They rather represent a minimum of the advised frequency for a caries-prone study population of young adults in the age range of 14+ years.

Quantification of caries lesions is greatly facilitated by digital processing of the radiographs.¹⁵ The advantage of using digital images is that electronic contrast enhancement may aid in visualization of the complex image.¹⁶ Recently, subtraction radiography was reported to be more accurate and reproducible for detecting mineral loss than subjective comparison of paired digital images.¹⁷ A digital subtraction program will be used to detect the differences in extent and density of the lesion. These programs have been successfully used to detect simulated and clinical caries progression.¹⁷⁻¹⁹

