11.4 Statistical Analysis

11.4.1 Descriptive Statistics

For the digital subtraction procedure, the ANOVA for Repeated Measures, will be used to determine significance between the two groups ($p=.05$). The remaining endpoints will be listed as percentages rather than subjected to statistical analyses.

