A previous infiltration study by Martignon et al. [5] reported a 3-year difference of proportions of 37.8% (95%CI: 20.5-55.2%) with (resin infiltration (68%) vs. control (30%)). Based on this and with alfa = 0.05 and a power of 80% the calculated sample size (t-test; matched pairs) would be 23 lesion pairs (thus 23 participants) to find significant differences. However, this study aimed to enroll 150 participants to not only allow for a potentially high attrition rate (20%) over a period of 3 years, but also aiming to better quantify the efficiency of the treatment effect.

Statistical Analysis

All evaluations are performed by two trained and calibrated examiners. The primary outcome is proportion of lesions that required restorative treatment (filling) after 3 years as measured via dental examination. Differences between groups will be tested using Fisher's exact test and ANOVA for Repeated Measures for subgroup analysis based on caries risk. Secondary outcomes are change in categorical lesion depth (progression to next depth category lesion; E1->E2->D1->D2->filling) after 6 months and 1, 2 and 3 years as measured by pairwise comparison of radiographs as well as the influence of Icon treatment on clinical parameters. Differences will be analyzed with McNemar's test with 95% confidence interval (95% CI) and P = .05.

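### The protocol tests the subtraction reading of the radiographs and the SAP tests a pairwise comparison of them, and no readable text says which one decides

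*Combined protocol and SAP*

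**What the plan says.** Protocol 11.4.3 defines a single radiographic outcome: "The outcome variable will be the caries progression status (regression, no changes or progression) for the selected lesions after 3 years". It then has that outcome read twice: "The radiographs will be read by 2 methods (1) visual independent reading and (2) subtraction radiography of digitized images". The principal investigator makes the visual reading. An external examiner views the subtraction images 10 days later.

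The two documents then test different things.

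- **Protocol 11.4.1:** "For the digital subtraction procedure, the ANOVA for Repeated Measures, will be used to determine significance between the two groups", at .05. For everything else, which includes the visual reading, "The remaining endpoints will be listed as percentages rather than subjected to statistical analyses".
- **SAP, Statistical Analysis:** change in depth category along E1, E2, D1, D2 and filling, "as measured by pairwise comparison of radiographs as well as the influence of Icon treatment on clinical parameters". The test is given as: "Differences will be analyzed with McNemar's test with 95% confidence interval (95% CI) and P = .05". Subtraction does not appear.

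The rank differs too. Protocol 6.2 lists radiographic change in lesion size (Specific Aim II) among the primary endpoints. The SAP makes depth change secondary, behind fillings at 3 years.

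Protocol 8.1 also indicates that the two methods perform differently: "subtraction radiography was reported to be more accurate and reproducible for detecting mineral loss than subjective comparison of paired digital images".

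**The concern.** Each document tests the reading that the other leaves untested. An analyst who follows both will have two p-values, each judged at .05, for whether infiltration slows radiographic progression (Specific Aim II and Hypothesis II). No readable rule says which p-value answers the question. A claim could rest on whichever reading is significant, and a split result would leave the trial with two answers.

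The readings can differ. Different people make them, on different images and by different criteria: a status code from 1 to 5 for the visual reading, and black, white or grey appearance for subtraction. The only disagreement rule in the readable text (9.5) asks assessors to reach consensus before the patient leaves a recall visit. It cannot settle a difference between two image readings made 10 days apart.

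**Working it through.** **Inputs from the documents.** Protocol 11.2 gives 150 participants and about 20% loss: 150 × (1 − 0.20) = 120 pairs, which reproduces the stated figure. The significance level is .05 in 11.4.1 and .05 in the SAP; sidedness is not stated and is taken as two-sided. The SAP's calculated 23 pairs plays no part in this point.

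**Inputs assumed.** The documents give no agreement between the two readings, no within-pair correlation and no reading error. All three are assumptions, shown as ranges.

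**Step 1: bounds.** Suppose either of two tests of size 0.05 may carry the claim.

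- Independent tests: 1 − (1 − 0.05)² = 1 − 0.9025 = 0.0975.
- Tests that always agree: 0.05.

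**Step 2: correlated tests.** With bivariate normal statistics Z₁ and Z₂ at correlation r, the chance of at least one false positive is 1 − P(|Z₁| < 1.96 and |Z₂| < 1.96).

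| r between test statistics | P(at least one false positive) |
|---|---|
| 0 | 9.75% |
| 0.5 | 9.1% |
| 0.8 | 7.8% |
| 0.9 | 7.0% |
| 1 | 5.0% |

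**Step 3: simulation with no treatment effect, 120 pairs.**

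- *McNemar on both readings.* With 40 to 50% progression, a within-pair latent correlation of 0.3 and independent misreading of 5 to 20% per method (kappa between methods about 0.8 down to 0.36), the chance of at least one p ≤ 0.05 is 7.6 to 9.5% with asymptotic tests and 5.7 to 7.3% with exact tests.
- *Half of the misreads shared.* This is plausible because both methods use the same radiographs. The figures fall to about 7.2 to 8.4% asymptotic and 5.4 to 6.4% exact.
- *Closer to the stated tests.* One reading was tested by a paired t-test, equivalent to a two-condition repeated-measures ANOVA at 3 years, and the other by McNemar, with 50% progression and no within-pair correlation. The result is 9.0% at kappa 0.49, 8.7% at 0.64 and 8.0% at 0.81. In these runs one reading was significant and the other not in 8.1%, 7.4% and 5.7% of trials.

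**Step 4: after the change.** With one deciding reading, the rate returns to 5%. If both readings stay tested at 0.025 each, it is at most 0.025 + 0.025 = 0.05. The cost of splitting depends on the true effect. Power is Φ[(d√n − z√ψ)/√(ψ − d²)], with n = 120, d the paired difference and ψ the discordant proportion.

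- At the planning difference (d = 0.38, ψ = 0.572 assumed), power exceeds 99.9% at either level.
- At an assumed d = 0.15 and ψ = 0.35, level 0.05 gives (1.643 − 1.160)/0.572 = 0.845, or 80%. Level 0.025 gives (1.643 − 1.326)/0.572 = 0.554, or 71%.

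**The case against.** A reader might infer that the plan contains two confirmatory tests of one endpoint. It does not. Within the protocol the visual reading is descriptive; within the SAP there is one radiographic analysis, and it is secondary. The second chance arises only because both documents apply and neither is given precedence. This objection stands, and it limits the point to a contradiction between the documents.

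A reader might also infer that the plan has no rule at all. That goes too far. Sections 8.1 and 11.4.3 both carry a notice that Amendment 1 revised them, and its pages are not shown. It may name a lead reading. The mismatch between 11.4.1 and the SAP is visible either way.

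Nor does the SAP state that its pairwise comparison is the protocol's visual reading. Section 11.4.3 calls that reading independent, yet also has the examiner judge the right-hand image against the left. The identification is likely but remains an inference.

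It is tempting to add that only the visual reading can yield the SAP's categories. This is only partly supported. Section 11.4.3 has lesion depth recorded visually, but the status code is not a depth category: a lesion that expands within E2 is scored as expanded without changing category.

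Finally, the inflation depends on assumed agreement. If the effect is as large as the 3-year rates cited in 4.3.4 (32% against 70%), a simulation with 120 pairs gave split verdicts in only 0 to 0.2% of trials at 0 to 10% misreading, rising to about 8% at 20%. Ambiguity would then be rare unless reading error is high. The risk lies in a null or modest effect.

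**Conclusion.** The point holds as a contradiction between stated rules: the protocol and the SAP test different readings of the same 3-year outcome, and no readable text reconciles them. If either reading may carry the radiographic claim, the false-positive rate for that outcome is above 5% for tests of nominal size, unless the two always agree, and cannot exceed 9.75% under normal theory. With 120 pairs it is about 7 to 9.5% (asymptotic McNemar) or 5.4 to 7.3% (exact McNemar). The direction does not depend on the assumed agreement; the size within those limits does. The inflation is moderate. It touches a primary endpoint under the protocol and a secondary one under the SAP, and leaves the SAP's primary outcome untouched. The change should be made, subject to what Amendment 1 says.

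**What to change.** First check whether Amendment 1 names a deciding reading. If it does, carry that rule into 11.4.1 and the SAP. If it does not, state in 11.4.1, 11.4.3 and the SAP that one 3-year reading, analysed by one paired test, decides the radiographic outcome.

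Which reading leads is the sponsor's choice. The current SAP text points to the visual reading; in that case analyse the E1/E2/D1/D2 depth recorded from each radiograph, not the 1 to 5 status code, and remove the subtraction significance test from 11.4.1. If subtraction is chosen, reword the SAP outcome to match what subtraction measures.

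Report the other reading as supportive: paired percentages with a 95% CI and a cross-table of agreement between methods, with no separate significance claim. State that a split result is reported as such and that the deciding reading governs the conclusion.

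The cost is wording only. Both readings are still made and no data are lost. The downside is that the supportive reading loses its formal test. Splitting alpha at 0.025 each would keep both tests, at the power cost shown above.

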8.4.2 Inclusion Criteria

In order to be eligible for the study, each participant must meet preliminary eligibility criteria and the participant or the guardian must be willing to sign a statement of informed consent. This will document the agreement of the participant to participate in the study activities. The patient must have two lesions which meet criteria as listed in Table 8.4.2, shown below.

Additionally, participants will be asked by study personnel not to participate in any other therapeutic research studies during the participant's follow-up period from baseline to the 36 month visit.

Table 8.4.2. Criteria used in the radiograph examination

E1	Radiolucency confined to the outer half of enamel
E2	Radiolucency involving the inner half of enamel
D1	Radiolucency in the outer third of dentin
D2	Radiolucency in the middle third of dentin
D3	Radiolucency in the inner third of dentin
D4	Tooth must have proximal contact
D5	Patient must be able to tolerate procedure (ie – Jaw-opening must be adequate)
D6	Tooth must have adequate attachment
D7	Tooth must be vital and not sensitive to palpation or percussion
D8	Tooth to be restored must occlude with an articulating surface
D9	Tooth must not be fractured or otherwise "non-restorable"

[figure not shown]

Figure 3: DMG criteria for treatment planning for Icon infiltration therapy. Adopted from DMG, Hamburg, Germany.

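### Section 11.4.3: on ordinary greyscale polarity the stated subtraction order and the black/white reading key have opposite signs, and no inversion is stated that would reconcile them

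*Combined protocol and SAP*

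**What the plan says.** Section 11.4.3 of the protocol describes two radiographic readings, one visual and one on digital subtraction images. For the second it gives the order of subtraction: "The subtraction images will be obtained by subtracting the follow-up from the baseline images of each lesion". The reading key comes later in the same section: "The subtraction progression will be observed as the presence of black points corresponding to an extension of the proximal lesion". It continues: "Conversely, regression will correspond to the presence of white points and stabilization as an evenly grayish appearance on the image".

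Table 8.4.2 grades lesions by radiolucency, the shallowest grade being "Radiolucency confined to the outer half of enamel". The source images are 8-bit greyscale files. Between the source images and the reader's screen, section 11.4.3 lists alignment, a density step ("The difference in density between the two images will then be normalized"), subtraction and a contrast stretch.

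Two people are involved. On production: "The digital subtraction of the digitized images will be undertaken by one of the examiners by means of the Compare software". On reading: "the subtraction images will be viewed by an external trained examiner 10 days after the visual assessment of conventional radiographs".

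Section 11.4.1 reserves significance testing for the subtraction result, by repeated-measures ANOVA; the other endpoints are to be given as percentages. Specific Aim II (section 6.2.2), listed under the primary endpoints, is change in lesion size on radiographs. The SAP takes fillings at three years as its primary outcome and depth category, from pairwise comparison of radiographs, as a secondary outcome. It does not mention subtraction.

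Section 11.4.3 is marked as revised by Amendment 1. The text of that amendment is not shown in the file.

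**The concern.** A radiolucent lesion is dark on an ordinary radiograph. When it extends, the affected area is darker at follow-up than at baseline, so baseline minus follow-up is positive and shows lighter than mid-grey. The key assigns light areas to regression. Read in the ordinary way, the sentence that makes the image and the sentences that interpret it point in opposite directions.

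The description of the pipeline is detailed, down to scanner model, file dimensions and monitor size, yet it does not say which end of the pixel scale is black or how the software displays a difference. The source of the images is not settled either: sections 9.4.1 and 9.4.2 describe a digital sensor, while section 11.4.3 digitizes conventional radiographs. The polarity cannot safely be taken for granted.

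The direction of the one comparison that the protocol tests is at stake. The planned quality check would not reveal an error of sign: the 25% reread measures agreement within the same examiner, and a systematic inversion would reproduce perfectly. The external examiner may consult the conventional baseline radiograph to locate the lesion; access to the follow-up radiograph is not mentioned.

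**Working it through.** The plan gives no figure to reproduce; the question is the sign of an image difference.

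**Inputs from the documents.** Order: baseline minus follow-up. Key: dark is progression, light is regression, even grey is stable (all section 11.4.3). Lesions are radiolucent (Table 8.4.2). Images are 8-bit, with values from 0 to 255.

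**Assumed for illustration.** Mid-grey offset 128. On an ordinary scale (0 is black) a progressing site goes from 150 to 110, a regressing site from 110 to 150, and a stable site stays at 130. Only the direction of change matters, not these values.

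**Formulas.** Displayed grey = 128 + (first image − second image). Inverted pixel scale: replace each value v by 255 − v, so 150 becomes 105 and 110 becomes 145. Inverted display: replace the displayed grey g by 256 − g.

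| Pixel scale | Display | Order | Progressing site | Regressing site | Agrees with key |
|---|---|---|---|---|---|
| Ordinary | Ordinary | Baseline − follow-up (as written) | 128 + (150 − 110) = 168, light | 128 + (110 − 150) = 88, dark | No |
| Inverted | Ordinary | As written | 128 + (105 − 145) = 88, dark | 128 + (145 − 105) = 168, light | Yes |
| Ordinary | Inverted | As written | 256 − 168 = 88, dark | 256 − 88 = 168, light | Yes |
| Inverted | Inverted | As written | 256 − 88 = 168, light | 256 − 168 = 88, dark | No |
| Ordinary | Ordinary | Follow-up − baseline | 128 + (110 − 150) = 88, dark | 128 + (150 − 110) = 168, light | Yes |
| Ordinary | Inverted | Follow-up − baseline | 256 − 88 = 168, light | 256 − 168 = 88, dark | No |

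A stable site gives 128 in every row. The order as written matches the key when exactly one inversion is present, and conflicts with it when there is none or two. Normalisation and contrast stretching, as ordinarily done, alter the size of the difference but not its sign.

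**Consequence if a full swap occurred.** Protocol section 4.3.4 cites three-year progression of 32% in infiltrated and 70% in control lesions, a difference of 32 − 70 = −38 percentage points in favour of infiltration. With the labels swapped, those 32% and 70% would be recorded as regression, and the same −38 points would appear to favour control.

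The recorded progression difference would become the true regression difference, which the documents do not give. Under assumed regression rates (infiltrated, control) of (0%, 0%), (5%, 5%), (10%, 5%) and (20%, 5%), it would be 0, 0, +5 and +15 points.

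**The case against.** The strongest answer is that the conflict rests on a polarity that the plan never states. Section 11.4.3 speaks of density and of scanned conventional radiographs. If pixel values represent film density, a radiolucency has a high value and the two statements agree. An inverted display has the same effect. This stands: the text does not prove that either statement is wrong. It does not remove the point, because that inversion has to be assumed, and on the ordinary reading of an 8-bit greyscale image the order and the key conflict.

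Second, nobody applies both statements. One examiner makes the image in the software and another scores it with the key alone. Scores are reversed only if the actual output shows progression as light, which the prose cannot settle. This also stands.

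Third, the same lesions are read visually before the subtraction reading, so a systematic inversion would appear as widespread disagreement between the two sets of scores. The data for detection would exist, but the plan specifies no comparison of the two methods and no rule for resolving a difference.

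A reader might infer that the radiographic endpoint as a whole, or the trial's main result, would come out reversed. The documents do not support that. The visual reading does not depend on the subtraction sign. The SAP's primary outcome is fillings found at dental examination, and its depth-category outcome does not name subtraction.

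**Conclusion.** The point holds as an unreconciled conflict of sign within section 11.4.3, conditional on ordinary polarity: radiolucency at the low end of the pixel scale and no inversion of scale or display. Under those conditions, images produced in the stated order and read with the stated key would have progression and regression swapped in the subtraction reading and in the ANOVA that protocol section 11.4.1 applies to it for Specific Aim II.

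The 38-point figure describes a complete and undetected swap at the cited rates. It is a worst case, not an expected effect. No reversal is demonstrated, because the software's actual output polarity is not stated. Nor can it be checked whether the current wording matches Amendment 1, since that text is not shown. The point still deserves action before scoring, because it concerns the direction of the only comparison that the protocol tests and costs almost nothing to settle.

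**What to change.** Test first, then word the section. Before any subtraction image is scored, take one image pair in which a known area has been artificially darkened at follow-up, run it through the Compare software exactly as planned, and see whether that area appears dark or light. File the output with the study records.

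Then state pixel polarity, subtraction order and display convention together in section 11.4.3, so that progression appears black as the key requires. If the test confirms ordinary polarity with no inversion, the order should read follow-up minus baseline. If the output of the present order already shows progression as black, keep that order and state the inversion responsible. Changing the order without the test could create the very swap it is meant to prevent, as the last row of the table shows. Check the new wording against Amendment 1.

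The cost is one sentence and one test pair through software already in use. Sample size, visits and the other outcomes do not change.
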